7.2 Period of Observation and Documentation

Adverse events (AEs) will be ascertained by the investigators using non-leading questions, noted as spontaneously reported by the patients to the medical staff or observed during any measurements on all study days. The observation period begins with the first administration of the IMP and ends with visit 4, (i.e. 6 months after day 1 [= first day of treatment with standard therapy]). The patient or his primary care physician should report any AE during the outpatient period via phone to the investigator.

AEs will be documented in the patient file and in the CRF. All subjects who present AEs, whether considered associated with the use of the study medication or not, will be monitored by the responsible investigator to determine their outcome; this applies to withdrawals too.

All SAEs and their relevance for the benefit/risk assessment of the study will be evaluated continuously during the study and for the final report. All SAEs will be documented in the "Serious Adverse Event" form (see 7.3).

Withdrawals allowing use of routinely recorded data (see 4.4.1)

If a patient withdraws from study participation but the persons having care and custody agree in writing that data routinely recorded by a physician not taking part in the INTENT study can be used for INTENT the following procedure is established:

The observation period for AEs ends 6 months after day 1 (same as for non-withdrawals). Adverse events reported via the physician will be recorded in the eCRF by the study site. AEs that are serious will be marked in the eCRF but not reported via SAE forms.

For a regular assessment of the benefit-risk-ratio SAE listings of these withdrawals will be generated by the data management every 3 months and forwarded to the Second Assessor (see 7.4). The Second Assessor documents review of the data and forwards the assessment to the KKS Heidelberg ([contact] or e-mail to [contact]). If the benefit/risk assessment is changed the Coordinating Investigator will be informed promptly and adequate measures will be initiated.

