7.1.5 Suspected Unexpected Serious Adverse Reaction (SUSAR)

SAEs that are both 'suspected', i.e., possibly related to the study drug (investigational medicinal product (IMP)) and 'unexpected', i.e., the nature and/or severity of which is not consistent with the applicable product information are to be classified as Suspected Unexpected Serious Adverse Reactions (SUSARs).

In case, either the investigator who primary reported the SAE or the second assessor, classifies the SAE as 'suspected' [either as 'definitely' or 'probable' or 'possible' related to IMP or 'not assessable'] and the SAE is unexpected the event will be categorized as a SUSAR.

All SUSARs are subject to an expedited reporting to the responsible ethics committee(s), the competent authority and to all participating investigators.

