7.3 Reporting of Serious Adverse Events by Investigator

All SAEs must be reported by the investigator to the Department of Pharmacovigilance at the KKS Heidelberg within 24 hours after the SAE becomes known using the "Serious Adverse Event" form. The initial report must be as complete as possible including details of the current illness and (serious) adverse event and an assessment of the causal relationship between the event and the study medication.

The reporting will be performed by faxing a completed 'SAE Form' to the KKS Heidelberg:

[contact]

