7.4 Expedited Reporting

SUSARs are to be reported to the responsible ethics committee, the competent authority (BfArM) and to all participating investigators within defined timelines, i.e. they are subject to an expedited reporting.

All SAEs will be subject to a second assessment by a designated person or his deputy, who will be independent from the reporting investigator.

The second assessor will fill out a 'Second Assessment Form' for each SAE and send it back per fax to the responsible person at the KKS Heidelberg within 48 hours:

Fax-number: [name]

The 'Second Assessment Form' will contain the following information:

- I) assessment of relationship between SAE and IMP (causality)
- II) assessment of expectedness of SAE (SmPC)
- III) statement if the benefit/risk assessment for the study did change as a result of SAE.

The expedited reporting (to competent authority, responsible ethics committee and investigators) will be carried out by a responsible Safety Officer at KKS Heidelberg. Fatal and life-threatening SUSARs must be reported without delay, but not later than 7 calendar days after becoming aware of the minimum reporting criterias. SUSARs that are not fatal or life-threatening must be reported without delay, at least within 15 calandar days after becoming aware of the minimum reporting criterias. Only SUSARs occurring after administration of IMP will undergo expedited reporting.

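### For children who leave the study but allow use of routine data, section 7.2 keeps serious events off the SAE form and passes them on only every 3 months, so expedited SUSAR reporting cannot be assured

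*Protocol*

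**What the plan says.** The general rules carry no exception.

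- Section 7.2 puts every SAE on the SAE form and has SAEs evaluated on a continuing basis.
- Section 7.3: "All SAEs must be reported by the investigator to the Department of Pharmacovigilance at the KKS Heidelberg within 24 hours" of learning of them, on that form.
- Section 7.4 gives every SAE an independent second assessment, returned within 48 hours. The form for it covers causality, expectedness and any change in benefit/risk. On onward reporting: "Fatal and life-threatening SUSARs must be reported without delay, but not later than 7 calendar days" after awareness of the minimum criteria; other SUSARs have 15 calendar days.
- Section 7.1.5: "All SUSARs are subject to an expedited reporting". Section 10.7 repeats this for SUSARs arising during the study.

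The last part of section 7.2 then covers children who leave study participation with written agreement to the use of routine data. Their AE window still runs to 6 months after day 1. The site enters events reported by the outside physician in the eCRF. For the serious ones: "AEs that are serious will be marked in the eCRF but not reported via SAE forms". Instead, "SAE listings of these withdrawals will be generated by the data management every 3 months and forwarded to the Second Assessor", who documents a review. The coordinating investigator is told promptly if the benefit/risk assessment changes.

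**The concern.** Two rules in one chapter prescribe opposite handling of the same event. A site that learns of a serious event in such a child cannot both file the form (7.3) and refrain from filing it (7.2).

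The consequence goes beyond paperwork. A SUSAR must be both suspected and unexpected, and the protocol places the judgement of expectedness with the second assessor. For this group the only described path to that person is the quarterly listing, whose stated purpose is a periodic look at benefit and risk; 7.2 does not say that causality and expectedness are judged from it event by event. Section 7.5 relies on SAEs being held in the drug safety database as the basis for expedited notification, and no path from the eCRF mark into that database is given.

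These children may have taken study drug recently. Treatment runs to week 12 after day 1 and the AE window to month 6. A fatal or life-threatening unexpected reaction could be known to the site and still wait weeks for the assessment that makes it reportable.

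**Working it through.** The protocol states no figure on this point that could be reproduced, so the check compares the rules and then sizes the delay and the group.

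**1. Rules side by side**

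| Step | General rule | Withdrawn, routine data allowed (7.2) |
|---|---|---|
| Site report | SAE form, 24 hours (7.3) | Mark in eCRF, no form |
| Second assessment | Form for each SAE, 48 hours (7.4) | Review of a listing every 3 months |
| Expectedness | On the Second Assessment Form (7.4) | Not mentioned |
| SUSAR reporting | 7 or 15 days, all SUSARs (7.1.5, 7.4, 10.7) | Not mentioned, not lifted |

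The 24-hour rule cannot be met for this group, because it has to be met with the form that 7.2 excludes. The 7- and 15-day limits depend on when the clock starts. Section 7.4 starts it at awareness of the minimum criteria and does not say whose awareness counts.

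**2. Delay, if the clock starts at eCRF entry**

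Assumptions: entries fall uniformly over a listing cycle of T = 89 to 92 days, and the listing reaches the assessor at once.

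- Longest wait: T, about 3 months. Mean wait: T/2 = 44.5 to 46 days.
- Share reaching the assessor within d days: d/T. With T = 91: 7/91 = 7.7% and 15/91 = 16.5%.
- Share if the assessor then uses the full 48 hours: (d - 2)/T. With T = 91: 5/91 = 5.5% and 13/91 = 14.3%.

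Over T = 89 to 92 the first pair ranges over 7.6-7.9% and 16.3-16.9%. Under these assumptions roughly nine in ten events would miss 7 days and more than eight in ten would miss 15. These shares describe the route for any serious event; only those that prove to be SUSARs are subject to the limits.

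**3. Children exposed to the exemption**

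Inputs: 340 randomised; 10% drop-out (8.1) up to a maximum 20% loss to follow-up (8.2); 27 months per child (3.2); AE window of 6 months from day 1 (7.2). Assuming loss spread evenly over the 27 months:

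- 10%: 340 × 0.10 × 6/27 = 34 × 0.222 = 7.6, about 8.
- 20%: 340 × 0.20 × 6/27 = 68 × 0.222 = 15.1, about 15.
- At the 4% drop-out that 8.2 cites from the recent MMF study: 340 × 0.04 × 6/27 = 13.6 × 0.222 = 3.0, about 3.

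These are counts before consent to routine data and before asking who has a serious event. Losses that cluster early would raise them.

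**The case against.** The best defence is that 7.2 is a deliberate exception. It has its own subheading, reviewer and escalation path; the children have left the trial and are seen by a non-trial physician; and a specific rule usually limits a general one. This explains the missing form. It does not explain the SUSAR duty, which nothing lifts and for which no route is given.

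Other parts of the defence stand and limit the point.

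- **Deadlines.** A reader might infer that the 7- and 15-day limits are bound to be broken. The text does not support that: if awareness dates from review of the listing, they could formally be kept. What can be said is that they are not assured.
- **Causality.** It might seem that nobody judges causality until the listing. Section 7.1.7 requires the investigator to rate every AE after study drug and exempts no one, and under 7.1.5 that rating alone can make an event suspected. What waits is the independent assessment and expectedness.
- **Intolerance.** One might suppose that children who stop because they do not tolerate treatment are the ones exempted. Section 4.4.1 keeps those who only stop treatment in follow-up, under the normal rules.
- **Bias.** One might fear an uneven SAE comparison between arms. Section 8.4 compares rates of serious events, not rates graded by causality, and events marked in the eCRF can be counted without a form.
- **Numbers.** Applying 10-20% directly to 340 gives 34-68 children. That sets loss over 27 months against a 6-month window. In addition, 8.1 uses its second 10% for major protocol violations, which are not withdrawals.

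**Conclusion.** The contradiction is in the current text and should be resolved. For this group the 24-hour form rule cannot be followed, and timely expedited reporting of SUSARs cannot be assured, with a wait of up to about 3 months between eCRF entry and the listing. The mean wait of about 45 days and the low shares within 7 and 15 days rest on uniform entry and on a clock that starts at eCRF entry; the protocol fixes neither.

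The number of children is small: about 8-15 under even loss of 10-20%, about 3 at 4%, fewer after consent, and only those with a serious event count. The point concerns the safety of individual children and a reporting duty that the protocol sets itself. It does not touch the primary analysis. It merits amendment because a single missed fatal or life-threatening SUSAR would matter and the remedy is cheap.

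**What to change.** Reconcile 7.2 with 7.3 and 7.4 by replacing the exempting sentence with: *SAEs within the AE observation period that become known to the investigator are reported on the SAE form within 24 hours of becoming known, also for withdrawn patients.* Keep the 3-monthly listing as a completeness check.

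The cost is a change of protocol wording and a few extra forms. Some will be incomplete because the information comes from an outside physician; 7.3 already asks only for as full an initial report as possible. The change does not remove the delay before the site hears of an event. Under section 6.1 the investigator contacts the outside physician when a visit falls due, and visits 3 and 4 lie at 11 weeks and 6 months after day 1, about 15 weeks apart. The new sentence acts only from the moment the site knows, so it places no new duty on sites to search for events.

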7.3 Reporting of Serious Adverse Events by Investigator

All SAEs must be reported by the investigator to the Department of Pharmacovigilance at the KKS Heidelberg within 24 hours after the SAE becomes known using the "Serious Adverse Event" form. The initial report must be as complete as possible including details of the current illness and (serious) adverse event and an assessment of the causal relationship between the event and the study medication.

The reporting will be performed by faxing a completed 'SAE Form' to the KKS Heidelberg:

[contact]

7.4 Expedited Reporting

SUSARs are to be reported to the responsible ethics committee, the competent authority (BfArM) and to all participating investigators within defined timelines, i.e. they are subject to an expedited reporting.

All SAEs will be subject to a second assessment by a designated person or his deputy, who will be independent from the reporting investigator.

The second assessor will fill out a 'Second Assessment Form' for each SAE and send it back per fax to the responsible person at the KKS Heidelberg within 48 hours:

Fax-number: [name]

The 'Second Assessment Form' will contain the following information:

- I) assessment of relationship between SAE and IMP (causality)
- II) assessment of expectedness of SAE (SmPC)
- III) statement if the benefit/risk assessment for the study did change as a result of SAE.

The expedited reporting (to competent authority, responsible ethics committee and investigators) will be carried out by a responsible Safety Officer at KKS Heidelberg. Fatal and life-threatening SUSARs must be reported without delay, but not later than 7 calendar days after becoming aware of the minimum reporting criterias. SUSARs that are not fatal or life-threatening must be reported without delay, at least within 15 calandar days after becoming aware of the minimum reporting criterias. Only SUSARs occurring after administration of IMP will undergo expedited reporting.

7.5 Development Safety Update Reports (DSURs)

The sponsor will prepare annual Development Safety Update Reports (DSURs) for competent higher federal authority (BfArM) as required. The reference date for the calculation of the Data Lock Points is the "date of the initial approval of the study by the competent higher authority" (BfArM). The format of the DSUR is in accordance with the ICH guideline E2F "Note for guidance on development safety update reports".

For purposes of safety analyses the sponsor is responsible to record all AE in a clinical database. To ensure the basis for expedited and periodic notification of authorities, SAEs will be additionally recorded in the drug safety database.

8 BIOSTATISTICAL CONSIDERATIONS

This section describes the considerations underlying the choice of the sample size as well as the statistical methodology applied for the analysis of primary and secondary outcome variables. More details can be found in the statistical analysis plan which will be finalized prior to performing any analyses.

8.1 Sample Size Calculation

The sample size calculation is based on the primary efficacy endpoint "occurrence of treated relapse within 24 months after completion of the initial treatment". In the literature different information are given regarding the relapse rate for the control group receiving standard prednisone therapy. We have decided to assume a relapse rate of 51% according to Gipson et al. [8] which gives the worst case resulting in a conservative sample size estimation. The same rate is expected for the experimental group. If the relapse rate in the experimental group accounts to less than 15% above the relapse rate of the control group, this will be considered as clinically irrelevant based upon clinical judgment. Therefore the margin is set to δ =0.15. As the direction of the difference to be established is known for non-inferiority studies and as - due to the rareness of the disease and the related limited available number of patients - the study could otherwise not be performed with sufficient power, a one-sided significance level of 5% is applied. Testing at a one-sided significance level of α = 5% and aspiring a power of 80%, a total of 272 patients (136 per group) are required (calculations performed with AddPlan 6.0). To account for 10% drop-out rate and major protocol violations in a further 10% 340 patients will be randomized.

8.2 Compliance/Rate of loss of follow up

The nephrotic syndrome in children is mostly an acutely presenting disease, and parents are very concerned about their child. With standard prednisone treatment we observe an adherence to therapy of more than 95%. According to our previous experience in performing studies in pediatric nephrology we assume that a minimum of 85% of patients assessed for eligibility will be allocated to study [4,5,19]. Due to the exclusive care of these patients in specialized pediatric nephrology centers we calculate with a loss of follow-up of maximum 20% which corresponds to our previous studies [4,5,19]. The recent study of the GPN, showing that MMF is efficacious in sustaining remission in children with frequently relapsing nephrotic syndrome, had only a drop-out rate of 4%. Therefore, for the entire study, we estimated 400 children with steroid-sensitive nephrotic syndrome to be assessed for eligibility, 340 to be allocated to study and 272 patients to be analyzed per protocol. However, in cases of premature withdrawal by a patient the persons having care and custody of this patient will be asked for informed consent so that routinely recorded data by the responsible physician can be used for the INTENT study. In this manner as many data as possible are recorded for evaluation of treatments in this rare disease.

8.3 Analysis Populations

The primary analysis will be performed for both the per-protocol population (PP) and the intention-to-treat population (ITT). The PP population comprises all patients, who were treated according to the randomized treatment as outlined in the protocol without major protocol violations (e.g., reduction of study medication of >50% or interruption of study medication of >3 days, violation of in- or exclusion criteria). The ITT population will compromise all patients randomized into the study. In this set, every patient is analyzed according to the group randomized into.

Since there may be patients who withdraw from the study after the treatment period or within the treatment period but consent to the incorporation of routinely recorded data was given the inclusion of these patients into the ITT population will be decided case by case before database lock and defined when writing the SAP. As appropriate, a third population will be defined for analysis of the primary and important secondary endpoints. How to deal with these patients and their data in detail depends on the time point of withdrawal and the amount and reliability of the routinely collected data.

The safety set will comprise all patients who have received study medication at least once, and will allocate the patients to the treatment they actually received, regardless of randomization. Whether routinely collected data of patients who withdraw prematurely can be included herein depends on the reliability of the collected safety data.

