8.4 Statistical Methods

The primary efficacy endpoint is the occurrence of a treated relapse within 24 months after completion of initial treatment. The non-inferiority of the experimental group *vs.* control group will be evaluated using the test according to Farrington and Manning [17]. The one-sided significance level is set to 5%.

The hypotheses to be assessed in the primary efficacy analysis are formulated as follows: H_0 : $p_MMF - p_Prednisone \ge \delta$ (δ =0.15, non-inferiority margin, see Section 8.1 Sample Size Calculation for justification)

 H_1 : p_MMF – p_Prednisone < δ , where p_* denotes the relapse rate in the respective group.

Before database closure the assignment of patients to the PP population (patients with no major protocol violations) and the ITT population (as classified by the intent-to-treat principle) are defined in the statistical analysis plan. The confirmatory analysis is performed for both the PP population and the ITT population. This approach reflects the equal importance of both analysis sets in a non-inferiority trial [29]. For the PP analysis missing values for the primary endpoint are not expected. In the ITT population missing values will be replaced according to Higgins [27]. As appropriate, a third population will be defined to adequately incorporate routinely collected data of patients who withdraw prematurely but gave informed consent for usage of routinely collected data. Details on inclusion of such data into sensitivity analyses of primary and secondary endpoints will be defined in more detail in the SAP. In case of uncertainty regarding data quality and reliablility these patients will only be analysed descriptively.

Additionally, binary logistic regression models will be performed as sensitivity analysis for the intervention comparison of the relapse rates adjusting for age, gender, center (grouped), and for results of therapeutic drug monitoring (grouped) based on different populations (PP, ITT, with values of drop-outs set to worst case).

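### Section 8.3 defines ITT as all randomised children, then lets ITT membership of withdrawn children with consented routine data be decided case by case

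*Protocol*

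**What the plan says.** Section 8.3 gives the definition: "The ITT population will compromise all patients randomized into the study", each patient analysed in the group to which he or she was randomised. (The verb is evidently meant as "comprise".)

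The next paragraph of 8.3 turns to children who withdraw during or after treatment and for whom use of routinely recorded data was agreed. For them, "the inclusion of these patients into the ITT population will be decided case by case before database lock", with the definition to follow in the SAP. How they are handled "depends on the time point of withdrawal and the amount and reliability of the routinely collected data". No threshold or rule is attached to these criteria. A third population may be defined as appropriate.

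Section 8.4 sets the role of the set: "The confirmatory analysis is performed for both the PP population and the ITT population", because both are held to be equally important in a non-inferiority trial. It restates that "the ITT population (as classified by the intent-to-treat principle) are defined in the statistical analysis plan". Missing primary outcomes in ITT are to be replaced by a cited method. Where the quality or reliability of routine data is uncertain, the children concerned are to be analysed descriptively only. Section 8.4 also gives everyone who prepares or changes the SAP access to blinded data only, and dates the SAP to the first year of recruitment.

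Section 6.1 lists relapse and its treatment among the routine data to be collected after withdrawal. Section 3.1 describes the trial as open.

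**The concern.** Doubt about a child's data can make the outcome missing. It cannot undo the randomisation. The two statements in 8.3 therefore cannot both hold: either every randomised child is in ITT, or some are admitted by individual decision.

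If both are followed, the result is also illogical. The case-by-case clause covers only withdrawn children with consent to routine data. A child who withdraws without that consent falls under the general definition and stays in with an imputed outcome. A child with a relapse documented by a physician may be left out or reduced to a descriptive listing. The child with more information has the weaker claim to membership.

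The PP set excludes protocol violators by design, so ITT is the only confirmatory set meant to preserve the randomised comparison. The material on which membership is judged contains the primary endpoint itself. Judging whether the data suffice is then hard to separate from the outcome: a recorded treated relapse settles a child's status at once, whereas a relapse-free child needs data to the end of the 24 months.

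**Working it through.** **1. The plan's own figure.** Section 8.1 gives 51% in both arms, margin 0.15, one-sided 5% and power 80%. Farrington-Manning restricted estimates under a difference of 0.15 are 0.5846 and 0.4346.

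- Null SD = √(0.5846·0.4154 + 0.4346·0.5654) = 0.699
- Alternative SD = √(2·0.51·0.49) = 0.707
- n per arm = [(1.645·0.699 + 0.842·0.707)/0.15]² = 135.3, so 136
- Total 272, and 272/0.80 = 340 randomised

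The stated 136, 272 and 340 reproduce. Power is 0.802 with 136 per arm and 0.873 with 170 per arm.

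**2. Set-up for the scenarios.** Take the null boundary, 66% (MMF) vs 51% (prednisone), with 170 randomised per arm. Expected relapsers are 0.66·170 = 112.2 and 0.51·170 = 86.7. Assume a fraction w1 of MMF children and w2 of prednisone children withdraw with routine-data consent, that withdrawal is unrelated to relapse within each arm, and that all withdrawn children with a given outcome are left out regardless of arm. The documents do not give these rates. Planned drop-out is 10% in section 8.1, and loss to follow-up is at most 20% in 8.2.

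If relapsers are left out, k1 = 112.2·w1 and k2 = 86.7·w2. The rates become (112.2 − k1)/(170 − k1) and (86.7 − k2)/(170 − k2), with difference D. If non-relapsers are left out, only the denominators shrink, by 57.8·w1 and 83.3·w2.

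Error = Φ[(0.15 − D − 1.645·S0)/S1], where S0 is the standard error from the restricted estimates and S1 the ordinary one.

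**3. Worked case, relapsers left out, 10% vs 5%.**

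- k1 = 11.22 and k2 = 4.34
- Rates 100.98/158.78 = 0.636 and 82.37/165.67 = 0.497, so D = 0.1388
- S0 = 0.0544 and S1 = 0.0545
- (0.0112 − 0.0895)/0.0545 = −1.44, so the error is 7.5%

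**4. Results.**

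| Withdrawal MMF / prednisone | Left out | D | One-sided error |
|---|---|---|---|
| any | nobody (full ITT) | 0.150 | 5.0% |
| 10% / 10% | relapsers | 0.152 | 4.6% |
| 10% / 5% | relapsers | 0.139 | 7.5% |
| 15% / 5% | relapsers | 0.125 | 11.6% |
| 10% / 10% | non-relapsers | 0.147 | 5.6% |
| 10% / 5% | non-relapsers | 0.160 | 3.3% |
| 5% / 10% | non-relapsers | 0.135 | 8.6% |

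Even selection that ignores the arm moves the error when withdrawal is unbalanced. The direction depends on which outcome is lost and in which arm.

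**5. Timing.** The SAP is due in the first year of recruitment. Recruitment runs 36 months (section 8.5), each child is followed for 24 months after treatment (3.2), and withdrawal is possible at any time (4.4.1). A first-year SAP can fix a rule, but it cannot settle individual cases that have not yet arisen.

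**The case against.** The clause is narrower than a quick reading suggests. It covers only withdrawn children with routine-data consent, places the decisions before database lock, and refers them to the SAP. SAP authors see blinded data only. The plan may have intended a choice about using the data rather than about membership, as its mention of a third population and of sensitivity analyses suggests.

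Much of this stands. Blinding lowers the risk, and no bias is shown. But the sentence speaks of including patients, not data. The blinding rule does not say that relapse outcomes are hidden or who takes the case decisions, and diary entries (MMF in ml, prednisone in mg, section 6.1) could reveal the arm.

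Stronger readings are tempting and are not supported:

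- *The clause biases towards non-inferiority in general.* The table shows errors both above and below 5%. If selection on data completeness keeps relapsers and loses non-relapsers, the error can fall.
- *The worst-case rule is anti-conservative.* The phrase "with values of drop-outs set to worst case" belongs to a sensitivity logistic regression, not to the confirmatory test, and its direction is not defined.
- *Replaced values enter the test as if observed.* The protocol cites a method and does not say this.
- *The statement on PP is part of the problem.* "For the PP analysis missing values for the primary endpoint are not expected" does not bear on ITT membership.

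The scenario errors also concern the ITT test alone. If both sets must succeed, trial-level error cannot exceed them.

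**Conclusion.** The contradiction holds on the text. The protocol itself fixes a discretionary entry rule for a confirmatory set that it defines as all randomised, so this is not a detail left open for the SAP. The case-by-case clause and the descriptive-only option both depart from ITT, and they treat children with data less favourably than children without.

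The size is conditional. The number of children concerned is unknown, and the 7.5% and 11.6% rest on assumed unbalanced withdrawal and on leaving out every withdrawn relapser. With balanced withdrawal the error stays near 5%. What is established is an avoidable inconsistency with a residual risk of outcome-related selection, not a demonstrated inflation of error.

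**What to change.** - In 8.3, delete the case-by-case decision on ITT membership. State that all 340 randomised children are in ITT without exception.
- In 8.4, remove the descriptive-only option as far as it concerns the ITT analysis.
- Fix one rule in advance, applied blind to arm and outcome, for when routinely recorded relapse data count as the primary outcome. Otherwise the outcome is missing and handled by the ITT imputation already named. State who applies the rule.
- Put alternative handling of doubtful routine data, including any third population, in sensitivity analyses.

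The Farrington-Manning test, margin and sample size do not change; power with 170 per arm remains 0.873 under the planning assumptions, taking outcomes as known for all. The cost is protocol and SAP wording and a little programming. Replacing the test by a Kaplan-Meier estimate, or requiring a worst case that runs in opposite directions in the two arms, is not needed for this point and has costs of its own. With 51% in both arms and 10% drop-out, the opposed worst case gives 0.9·0.51 + 0.10 = 55.9% vs 0.9·0.51 = 45.9%, an artificial difference of 10 points against a 15-point margin.
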